Cover Page for Study Protocol Document

Official Study Title: What makes people better at retrieving proper names?

NCT05550779

Document Date 9/5/24

Research Summary and Participant Information

Research purpose/significance

Provide a brief background and describe the major research question/s of the proposed study in language that can be understood by an individual outside your discipline.

This study tests the relationship between proper name retrieval, age, and a brief mindful breathing exercise intervention. Older adults demonstrate more tip-of-the-tongue (TOT) states compared to younger adults. Mindful breathing exercises are suggested to reduce anxiety and increase attentional functioning; therefore, improve cognitive performance. Overall, I expect that older adults will report more TOT states compared to the younger adults. Additionally, both old and younger adults in the mindful breathing exercise condition (compared to the control condition) should have a decrease in TOT states. This study will test the age effect on TOT rate as well as the magnitude of improvement following a mindful breathing exercise between old and younger adults.

Does this study only involve existing data and no living participants?

No

Methodology

Describe, in narrative format, the research design (descriptions of methods) and list procedures to be used.

The study will test 120 participants, 60 younger adults (ages 18-35) and 60 older adults (ages 60-80). All participants will be treated following the ethical guidelines of the American Psychological Association, and the first step will be providing informed consent to participate. Participants in the mindful breathing exercise condition will listen to a 10-minute guided

meditation presentation. The presentation instructs participants to engage in breathing exercises, and includes music intended to be calming, with binaural beats, which have been found to provide a benefit beyond other mindfulness components. Participants in the control condition will listen to a 10-minute clip of a narration of a story about a scientist's experience on a planet who attempts to communicate with an extraterrestrial being. A mindfulness self-report rating will be asked after the clip.

Then participants will participate in a name retrieval task in which they will be shown 83 images of celebrities. They will be asked to either retrieve the name the celebrity in the image, say they don't know who the person is, or say the name is on the tip of their tongue. Once all images are shown, the mindfulness self-report rating will be administered once again. After, the participants will be shown the images in which they said they were experiencing a TOT state and asked if the name of the person they were thinking of is the actual name of the person. Then participants will be shown all the images again with the celebrity's name underneath and will be given a familiarity rating of the celebrity in which they rate how familiar they are with the celebrity in the photograph.

For the younger adult participants, after the familiarity rating is completed, the researcher will post in the Zoom chat a Qualtrics link to complete the second part of the study. The researcher will end the Zoom videoconference call and the participants will complete the second part of the study on their own. The second part of the study includes a demographics form, trait mindfulness scale (MAAS), post-study questionnaire (including questions regarding the purpose of the study and meditation habits), and a debriefing of the study.

However, for the older adult participants, after the familiarity rating is completed, the researcher will administer the Mini-Mental State Exam (MMSE; Folstein et al., 1975). Once the MMSE is complete, the older adult participants will receive the Qualtrics link via the Zoom chat, the researcher will end the Zoom videoconference call, and the participants will complete the second part of the study on their own. Data from anyone scoring fewer than 26 out of the maximum score of 30 on the MMSE will be excluded from the analyses with the resulting sample characterized as non-demented elderly.

Do you plan on conducting this research project in person (face to face) with participants?

No

Additional Interaction Information

Is the information recorded in such a manner that subjects can be identified, directly or indirectly or through identifiers linked to the subject?

Yes

Would the disclosure of subjects' responses outside the research place the subjects at risk of criminal or civil liability or be damaging to the subjects' financial standing, employability, insurability, or reputation?

No

Does this protocol involve the use of medical equipment (i.e. X-rays, PET scans, MRI, etc.) on participants? This would include any methods that add energy into the body or that could possibly increase risk or harm.

No

Does the research involve ANY of the following populations?

Research involves NONE of the populations listed

Participant Recruitment

Describe how participants will be *selected* and *rationale* for the selection criteria.

Because this study compares performance for young and older adults, people 18-35 or 60-80 years of age can participate. They must be native, fluent speakers of American English because the project tests aspects of language production that differ for speakers of different languages. They also must have resided in the United States (US) for at least 5 years so they are familiar with the celebrities shown in the name retrieval task.

Describe from where the participant population will be drawn. Include when, where, and how the potential participants will be recruited.

Young adults will be recruited utilizing the UCCS Psychology Department SONA System, and older adults will be recruited utilizing UCCS's community research volunteer list that includes many adults ages 60-80 (contacted via phone or email). If necessary, additional recruitment will occur via flyers or other advertisements (those materials will be submitted to the IRB before posting, if needed).

Participant Enrollment Detailed Information

Participant Enrollment Information

Participant	Estimated Total	Estimated Number of Participants	Estimated	Estimated Number of		
			Number of Participants	Number of Male Participants	Number of Female Participants	Non-Binary or Non-Categorizing Participants
Age Range						
Adults 18-65 years	60		No answer provided.	No answer provided.	No answer provided.	No answer provided.
Adults over 65 years	60		No answer provided.	No answer provided.	No answer provided.	No answer provided.

Describe how coercion or perceived coercion of research participants will be avoided for all research populations (i.e., provide detail regarding subjects who are students of, or supervised by, the investigator).

All participation is voluntary and individuals will be given the option to opt- out at any point during recruitment or during the study without any negative consequences. Compensation for this study is not large enough to be coercive, but adequately compensates participants for their time. Individuals known to the PI will not be targeted for recruitment.

Describe where the data will be stored, who will have access to the data, and measures taken to secure the data. Include procedures for maintaining participant confidentiality. For any hardcopy data, CD, tapes, specimens, etc., describe any physical safeguards that will be in place; for example, locked cabinet/office, data de-identified, encryption, approved cloud storage (Dropbox is not permitted).

Data will be downloaded from Qualtrics and video recordings will be downloaded from Zoom onto the PI's password-protected computer. Only the PI and faculty advisor, [name], will have access to the data.

Describe how the privacy of the participants and the confidentiality of the data will be maintained (i.e., participants will be assigned an ID number to protect identity).

Video recordings from Zoom will be used for data scoring verification. Therefore, the recordings are identifiable. However, the name of the participant will be changed in the Zoom videoconference to arbitrary ID numbers to track participant data.

Are you accessing a database/data set that requires a privacy, confidentiality, or any other type of signed agreement in order to be granted access?

No

Describe the plans for the final disposition or de-identification of data that are identifiable in any way (directly or indirectly via codes) once the study has ended. If the data will be kept indefinitely, describe the format of the data and purpose of retention. If data will be destroyed, describe the timeline and method.

Once the data is verified using the video recordings, the video recordings will be permanently deleted. The data file (which includes no identifiable participant information) will be retained until 5 years following any publication that results from the research.

Name those who will identify, document, and report adverse or unanticipated events.

[name]

Risk and Benefit Analysis

Describe all benefits of the research (benefits to individual participants, society, and/or science). If none, state "none" in the space provided and in the informed consent document.

The study will give researchers a better understanding of how individuals' personal traits relate to their ability to produce proper names. There are no direct benefits to participants.

Describe all risks and potential risks (e.g. physical, mental, emotional, and/or legal) to the participants. All studies entail at least some risk (e.g. annoyance, frustration). [?](#)

Participants might feel frustrated by the name retrieval task, which was designed to be difficult.

Describe how the risks are reasonable in relation to the anticipated benefits.

The potential for frustration is minor compared to the knowledge to be gained.

Describe safeguards that will be taken to protect participants' rights, welfare, and reduce risks (e.g. medical consultation, counseling, etc.).

The consent form tells people that their participation "is entirely your choice. If you decide to take part, you can change your mind and stop participating at any time during the study session."

Is your study conducted virtually, or in some other manner, where participants will not provide a wet signature on a paper consent? (i.e. you need to request a waiver of documentation of consent, see help for details) [?](#)

Yes

Choose the most appropriate option:

Other

Other explanation

The consent form will be shown to the participant via Zoom videoconference call through the "Share Screen" option; therefore, the researcher will be the only one with control over the screen. The participant will read through the consent form and asks the researcher to scroll down on the page when the participant has finished reading through the sections on the screen. Once the participant reaches the end of the document, the researcher will say: "Now you've read through this document, please say out loud 'Yes, I consent' or 'No, I don't consent' and I will check the appropriate box." Then the participant will give verbal consent and the researcher will click on the appropriate option.

Are you requesting an alteration of informed consent (i.e. no consent, consent is altered to omit certain required elements)? [?](#)

No

Describe the consent process, including who will be obtaining the consent.

The consent form will be presented to participants prior to beginning the study.

Please describe the amount of time participants will be committing to, in order to participate in the study (i.e., 2 hours a week plus 30 mins travel to study site).

60-75 minutes

Will research participants be offered compensation for participating in the research?

Yes

Describe the nature of the compensation, including dollar value and schedule of payment. This information should also be stated in the informed consent document.

2.5 points of SONA credit upon study completion for UCCS students (ages 18-35) and \$15 electronic gift card to non-student participants (ages 60-80).

Describe any plans to share results of the research with participants.

None

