Cover Page for Analysis Plan Document

Official Study Title: What makes people better at retrieving proper names?

NCT05550779

Document Date 9/5/24

Data analysis will be conducted using a two-way ANOVA for each of the TOT measures (TOTs/# familiar trials; TOTs/# known names TOTs/# unsuccessful retrievals) to determine significant main effects, interactions, and simple main effects between the variables. The proposed analysis will determine if there is a) a significant main effect of the manipulation on TOT rate, b) a significant main effect of age on TOT rate, and c) an interaction between mindfulness condition and age group on TOT rate. The two-way ANOVA will be conducted using SPSS (Version 28.0). First, main effects and interactions will be examined. If there is an interaction, simple main effects will be assessed using the Bonferroni adjustment.

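### Does describing the intervention as a mindful breathing exercise, when the clip also carries music and binaural beats, call for a change to the plan?

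*Protocol*

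**What the plan says.** In the protocol, the Research purpose/significance section opens with "This study tests the relationship between proper name retrieval, age, and a brief mindful breathing exercise intervention". Its mechanism is also put in terms of breathing: "Mindful breathing exercises are suggested to reduce anxiety and increase attentional functioning". The age question concerns "the magnitude of improvement following a mindful breathing exercise between old and younger adults". The hypothesis itself is a comparison of conditions: both age groups are expected to have fewer tip-of-the-tongue (TOT) states in the breathing condition than in the control condition.

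The Methodology section then says what the active condition contains. It is a guided meditation lasting 10 minutes that gives breathing instructions and "includes music intended to be calming, with binaural beats, which have been found to provide a benefit beyond other mindfulness components". For the comparator: "Participants in the control condition will listen to a 10-minute clip of a narration of a story". Nothing is said about whether that clip has music or beats under the narration.

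The SAP plans a two-way ANOVA for each TOT measure. It asks whether there is (a) "a significant main effect of the manipulation on TOT rate" and (c) "an interaction between mindfulness condition and age group on TOT rate". It does not restate what the two conditions contain.

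**The concern.** The stated aim and the stated mechanism both name breathing. The active clip bundles breathing instruction with two other elements, and the protocol itself credits one of them, the beats, with a benefit of its own. As described, the control has none of the three. A lower TOT rate in the active condition could then come from the beats, the music, the breathing or any mixture, and the analysis could not tell which. The same holds for a difference between age groups in the size of the improvement.

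Nothing collected in the study separates the components. The mindfulness self-report rating is taken after the whole clip and again after the naming task, and the SAP does not use it. The trait mindfulness scale and the meditation-habits questions describe participants, not parts of the clip. At stake is attribution: a positive result might be reported as showing that breathing helps name retrieval, on evidence that supports only a claim about the clip as a whole.

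**Working it through.** There is no stated figure to reproduce. The question is what the design can estimate.

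**Inputs.** Two conditions and two age groups (protocol, Methodology; SAP); three named components of the active clip (Methodology); 120 participants, 60 per age group (Methodology). The documents do not state the audio content of the control, so both cases are worked.

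**Case 1: the control has no music or beats.** Let B, M and T be the effects of breathing instruction, music and beats in younger adults. Let gB, gM and gT be the extra effects in older adults, A the age effect under control, and μ the mean for younger controls (the story effect is absorbed in μ). The cell means are:

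- younger, control: μ
- younger, active: μ + (B + M + T)
- older, control: μ + A
- older, active: μ + A + (B + M + T) + (gB + gM + gT)

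That is 8 parameters on 4 cells. The design matrix has rank 4, because the three component columns are identical (rank 1) and so are the three interaction columns (rank 1). The estimable quantities are:

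- active minus control in younger adults = B + M + T
- interaction (difference of the two differences) = gB + gM + gT
- main effect of condition (average over age groups) = (B + M + T) + ½(gB + gM + gT)

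B alone and gB alone are not estimable. Sample size does not enter, so more participants would not help.

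**Case 2: the control has the same music and beats.** M, T, gM and gT appear in both conditions and cancel. What remains is breathing and meditation guidance against story content. Most of the concern then disappears, though guidance and story still differ.

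**What the plan claims, set against this.** Question (a) in the SAP is the main effect of condition, and question (c) is the interaction. Both are estimable in either case. Neither document lists B or gB as a quantity to be estimated.

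**What isolating breathing would cost.** Suppose a third arm received the same music and beats without breathing instruction, and the total stayed at 120. Assume SD 1, two-sided α = 0.05 and equal allocation; the documents give none of these. Each contrast goes from 60 v 60 to 120/3 = 40 v 40.

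- Power at a difference of 0.5 SD, from Φ(0.5/√(2/n) − 1.96): n = 60 gives Φ(2.739 − 1.96) = 0.78; n = 40 gives Φ(2.236 − 1.96) = 0.61.
- Difference detectable with 80% power, (1.96 + 0.842) × √(2/n): 0.51 SD at n = 60 and 0.63 SD at n = 40.
- To keep 80% power at 0.5 SD: 2 × (2.802/0.5)² ≈ 62.8, so 63 per arm, or 3 × 63 = 189 in total.

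**The case for a change.** The strongest case for acting is that this goes beyond a loose label. The investigator says the beats add something beyond the other components, yet names only breathing in the purpose and the mechanism. The SAP's terms are undefined, so a reader goes back to the protocol and finds breathing. No sentence limits the interpretation, and the wording remedy would cost almost nothing.

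Some of this stands. The rationale sentence does speak only of breathing, the algebra in Case 1 is right, and a report that credited breathing alone would overreach. The documents also leave open which of the two cases applies.

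It does not amount to a fault in the plan. The form asks for the purpose in language for readers outside the discipline, and a short name for the condition is natural there. The operational definition follows in the Methodology section, where the music and beats are stated openly. The sentence about the beats itself treats the clip as having several components. With only two conditions in the study, the SAP's factor has one possible meaning. That a later report might overstate the result is conjecture about the report, and the same could be said of any two-arm test of a multi-component intervention.

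**Conclusion.** No change to the plan is needed. Followed as written, it gives a test of one audio clip against another, in two age groups, which is the comparison that the hypothesis states. Rewording the label would leave every estimate, p-value and sample size as they are.

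The one substantive alternative within two arms, playing the same track under the story, is a fair trade-off. It would remove music and beats from the contrast but still leave meditation guidance against story content, and it would answer a narrower question than the effect of the clip as delivered. A third arm would answer the breathing question, at the loss of power shown above. The study does not set out to do either.

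The remaining gap is small: the audio content of the control clip is not written down. The authors know it and can state it when they describe the clips, reading the condition effect as that of the clip as delivered.

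This conclusion rests on two points. First, non-estimability of breathing alone assumes a control without music or beats; if it has both, the concern largely falls away. Second, the conclusion covers only what the condition contrast means. The documents do not describe how participants are allocated to conditions; that bears on whether a difference can be credited to the clip at all, and is a separate question.

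### Does excluding older adults on an MMSE given after the clip and the name task bias the comparison of conditions?

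*Protocol*

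**What the plan says.** The Methodology section of the Protocol sets the order of the session: the 10-minute clip, a mindfulness rating, the 83-image name task, a second rating, the check of TOT responses and the familiarity rating. Only then, "for the older adult participants, after the familiarity rating is completed, the researcher will administer the Mini-Mental State Exam". The rule that follows is "Data from anyone scoring fewer than 26 out of the maximum score of 30 on the MMSE will be excluded from the analyses". The Protocol gives those who remain a label, and so has "the resulting sample characterized as non-demented elderly". Younger adults do not take the MMSE.

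Participant Recruitment has no cognitive criterion that applies earlier. It says "people 18-35 or 60-80 years of age can participate" and adds requirements on language and US residence.

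The SAP is one paragraph. It plans "a two-way ANOVA for each of the TOT measures", testing the main effects of condition and age and "an interaction between mindfulness condition and age group on TOT rate". It does not mention the MMSE, the number excluded by condition, or an analysis that keeps the excluded participants.

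**The concern.** Selecting the analysed sample on something measured after the intervention can undo the balance between conditions. The Protocol's own rationale supplies a route: "Mindful breathing exercises are suggested to reduce anxiety and increase attentional functioning; therefore, improve cognitive performance". The MMSE is a cognitive test taken in the same session. If breathing lifted a few low scorers over the cut-off, the mindful group would keep people whom the control group loses, and those people probably have more TOT states. A cut-off fixed in advance stops discretionary exclusion but does not stop this.

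Only older adults can be removed, so nothing in the younger group offsets the bias. It would enter the interaction in full and the main effect of condition by half. The interaction matters because the Protocol sets out to compare "the magnitude of improvement following a mindful breathing exercise between old and younger adults". As planned, the output would not let a reader see whether exclusions differed by condition.

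**Working it through.** **Inputs from the documents.** 60 younger and 60 older adults; exclusion below 26 of 30; MMSE after the outcome task; two-way ANOVA. The documents state no exclusion rate, MMSE distribution, MMSE-TOT correlation, allocation ratio, alpha or power, so there is no planned figure to reproduce.

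**Assumptions.** 30 per cell; two-sided alpha 0.05; share of control older adults excluded p = 5-20%; uniform clip effect on the MMSE s = -0.5 to +0.5 SD; size of the within-condition MMSE-TOT correlation rho = 0.3-0.7 (higher MMSE, fewer TOTs); no true effect of the clip on TOT.

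**Formula.** With a0 = Phi^-1(p) and h(a) = phi(a)/[1 - Phi(a)], those retained have a mean MMSE that exceeds their own condition's mean by h(a0) SD in control and h(a0 - s) SD in the mindful condition. The bias in the older-adult TOT difference (mindful minus control, in SD) is

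bias = rho x [h(a0) - h(a0 - s)].

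A positive value works against breathing; a negative value favours it.

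| p | s | h(a0) | h(a0 - s) | bias, rho 0.3 | bias, rho 0.7 |
|---|---|---|---|---|---|
| 5% | +0.5 | 0.109 | 0.041 | +0.020 | +0.048 |
| 5% | -0.5 | 0.109 | 0.237 | -0.039 | -0.090 |
| 10% | +0.5 | 0.195 | 0.085 | +0.033 | +0.077 |
| 10% | -0.5 | 0.195 | 0.376 | -0.054 | -0.126 |
| 20% | +0.5 | 0.350 | 0.178 | +0.052 | +0.120 |
| 20% | -0.5 | 0.350 | 0.594 | -0.073 | -0.171 |

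At s = 0 every entry is zero. A mid-range case (p = 10%, s = +0.3, rho = 0.3) gives 0.3 x (0.195 - 0.121) = +0.022 SD. The largest value is 0.7 x (0.594 - 0.350) = 0.171 SD, when the clip lowers the MMSE. If the clip raises it, the largest is 0.120 SD. The main effect of condition takes half: 0.085 and 0.060 SD.

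**Direction.** Under a uniform shift the sign follows the direction of the clip's effect on the MMSE. It can also reverse: in a simulation with an average MMSE gain of 0.3 point, a bias of 0.004-0.037 SD toward benefit appeared when people who gained more on the MMSE also gained more on TOT.

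**Against the precision of the tests.**
- Standard errors in SD units: interaction sqrt(4/30) = 0.365; main effect half of that, 0.183.
- Largest bias over standard error: 0.171/0.365 = 0.47, and the same ratio for the main effect.
- False rejection of the 1 df F test (116 error df) at that ratio: 7.5%. At 0.120 SD it is 6.2%.
- Detectable at 80% power: 1.03 SD (interaction) and 0.52 SD (main effect). The largest bias is 0.171/1.03 = 17% of the former, and the same share of the latter.
- For the older-adult simple effect the standard error is sqrt(2/30) = 0.258, so the ratio is 0.171/0.258 = 0.66. That comparison is made only if an interaction is found, and with a Bonferroni adjustment.

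**What added checks could show.**
- MMSE by condition, 30 per condition, assumed MMSE SD 1.5-2.0: the standard error is SD x sqrt(2/30) = 0.39-0.52 point, so the 95% half-width is 0.78-1.03 points. A 0.5 SD shift is 0.75-1.0 point. Power is about 48% for that shift and 12% for 0.2 SD.
- Fisher test of exclusions, 30 v 30: power about 2% for 10% v 5%, 10% for 20% v 10%, and 24% for 20% v 5%.
- Repeating the ANOVA with all tested older adults: with no bias at all, the two interaction estimates differ by chance with an SD of 0.07-0.17 (5-20% excluded, rho 0.3-0.7). The bias being sought is 0-0.17.

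**The case for a change.** The best argument for acting is cost. A sentence in the SAP, a table of exclusions and MMSE scores by condition, and one repeat of the same ANOVAs would use data already in hand, since both the name task and the MMSE are finished before anyone is removed. The claim that the bias is small rests on assumed inputs, and only the investigators will hold the data to examine it.

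The facts behind this argument stand, and so does the structural point that exclusion follows the intervention. What does not stand is that the additions would settle the matter. The chance gap between the two ANOVA runs is as wide as the bias. Including everyone also changes the population from the one the Protocol describes, so a discrepancy could be bias, chance or the added low scorers, and nothing would separate them. Asking whether the two runs agree on significance, across three TOT measures, would invite false alarms. Giving the MMSE before the clip would remove the dependence, but only older adults would then be tested before the outcome task, which introduces an age-group difference of its own.

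The route is also weak. The MMSE follows the name task, a second rating, the TOT check and a re-rating of all images. The model has a 10-minute clip shift that later, general screen while leaving the targeted outcome unmoved.

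**Conclusion.** The concern is sound in principle but calls for no change. The rule is set in advance with a fixed cut-off, it defines the intended older sample, and placing the MMSE last keeps the sequence up to the outcome the same in both age groups; this is a fair trade-off. The bias is zero unless the clip moves the MMSE. Under the assumed ranges it is at most about 0.17 SD in the interaction and 0.085 SD in the main effect, in a direction that cannot be established, with false rejection of at most about 7.5% instead of 5.0%. These limits rest on a uniform shift of no more than 0.5 SD, no more than 20% of control older adults excluded, a correlation of no more than 0.7, and 30 per cell; none of these figures is in the documents. Exclusion counts and MMSE scores by condition, and estimates for all tested older adults with confidence intervals, could reasonably appear as description in the report. They would alter neither the primary sample nor the planned tests, and could not confirm or rule out a bias of this size.
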